7.4. Gilead Reporting Requirements

Depending on relevant local legislation or regulations, including the applicable US FDA Code of Federal Regulations, the EU Clinical Trials Directive (2001/20/EC) and relevant updates, and other country-specific legislation or regulations, Gilead may be required to expedite to worldwide regulatory agencies reports of SAEs, serious adverse drug reactions (SADRs), or suspected unexpected serious adverse reactions (SUSARs). In accordance with the EU Clinical Trials Directive (2001/20/EC), Gilead or a specified designee will notify worldwide regulatory agencies and the relevant IEC in concerned Member States of applicable SUSARs as outlined in current regulations.

Assessment of expectedness for SAEs will be determined by Gilead using reference safety information specified in the investigator's brochure or relevant local label as applicable.

All investigators will receive a safety letter notifying them of relevant SUSAR reports associated with any study IMP. The investigator should notify the IRB or IEC of SUSAR reports as soon as is practical, where this is required by local regulatory agencies, and in accordance with the local institutional policy.

7.5. Special Situations Reports

7.5.1. Definitions of Special Situations

Special situation reports include all reports of medication error, abuse, misuse, overdose, reports of AEs associated with product complaints, occupational exposure with an AE, pregnancy reports regardless of an associated AE, and an AE in an infant following exposure from breastfeeding.

Medication error is any unintentional error in the prescribing, dispensing, or administration of a medicinal product while in the control of the health care provider, subject, or consumer.

Abuse is defined as persistent or sporadic intentional excessive use of a medicinal product by a subject.

Misuse is defined as any intentional and inappropriate use of a medicinal product that is not in accordance with the protocol instructions or the local prescribing information.

An overdose is defined as an accidental or intentional administration of a quantity of a medicinal product given per administration or cumulatively which is above the maximum recommended dose as per protocol or in the product labelling (as it applies to the daily dose of the subject in question). In cases of a discrepancy in drug accountability, overdose will be established only when it is clear that the subject has taken the excess dose(s). Overdose cannot be established when the subject cannot account for the discrepancy except in cases in which the investigator has reason to suspect that the subject has taken the additional dose(s).

Product complaint is defined as complaints arising from potential deviations in the manufacture, packaging, or distribution of the medicinal product.

Occupational exposure is defined as exposure to a medicinal product as a result of one's professional or non-professional occupation.

7.5.2. Instructions for Reporting Special Situations

7.5.2.1. Instructions for Reporting Pregnancies

The investigator should report pregnancies in female study subjects that are identified after initiation of study drug(s) and throughout the study, including the post study drug(s) follow-up period, to Gilead PVE by transmitting electronically and also by sending paper pregnancy report form within 24 hours of becoming aware of the pregnancy.

Refer to Section 7.3 and the eCRF completion guidelines for full instructions on the mechanism of pregnancy reporting.

The pregnancy itself is not considered an AE nor is an induced elective abortion to terminate a pregnancy without medical reasons.

Any premature termination of pregnancy (eg, a spontaneous abortion, an induced therapeutic abortion due to complications or other medical reasons) must be reported within 24 hours as an SAE. The underlying medical reason for this procedure should be recorded as the AE term.

A spontaneous abortion is always considered to be an SAE and will be reported as described in Section 7.1.2. Furthermore, any SAE occurring as an adverse pregnancy outcome post study must be reported to Gilead PVE.

The subject should receive appropriate monitoring and care until the conclusion of the pregnancy. The outcome should be reported to Gilead PVE using the pregnancy outcome report form. If the end of the pregnancy occurs after the study has been completed, the outcome should be reported directly to Gilead PVE. Gilead PVE contact information is as follows:

Email: PPD

Fax: PPD

Pregnancies of female partners of male study subjects exposed to Gilead study drug must also be reported and relevant information should be submitted to Gilead PVE using the pregnancy and pregnancy outcome forms within 24 hours. Monitoring of the subject should continue until the conclusion of the pregnancy. If the end of the pregnancy occurs after the study has been completed, the outcome should be reported directly to

Gilead PVE, fax number PPD or email PPD

Refer to Appendix 4 for Pregnancy Precautions, Definition for Female of Childbearing Potential, and Contraceptive Requirements.

7.5.2.2. Reporting Other Special Situations

All other special situation reports must be reported on electronic special situations report form and transmitted to Gilead PVE within 24 hours of the investigator becoming aware of the situation. If for any reason it is not possible to record the special situation report (SSR) information electronically, ie, the eCRF database is not functioning, record the SSR on the paper special situation reporting form and submit within 24 hours to:

Gilead PVE: Fax: **PPD**

Email: PPD

As soon as it is possible to do so, any SSR reported via paper must be transcribed into the eCRF.

Database according to instructions in the eCRF completion guidelines. These reports must consist of situations that involve study drug(s) and/or Gilead concomitant medications, but do not apply to non-Gilead concomitant medications.

Special situations involving non-Gilead concomitant medications does not need to be reported on the special situations report form; however, for special situations that result in AEs due to a non-Gilead concomitant medication, the AE should be reported on the AE form.

Any inappropriate use of concomitant medications prohibited by this protocol should not be reported as "misuse," but may be more appropriately documented as a protocol deviation.

Refer to Section 7.3 and the eCRF completion guidelines for full instructions on the mechanism of special situations reporting.

All clinical sequelae in relation to these special situation reports will be reported as AEs or SAEs at the same time using the AE eCRF and/or the SAE report form. Details of the symptoms and signs, clinical management, and outcome will be reported, when available.

8. STATISTICAL CONSIDERATIONS

8.1. Analysis Objectives and Endpoints

8.1.1. Analysis Objectives

The primary objectives of this study are:

- To evaluate the antiviral efficacy of therapy with SOF/VEL FDC for 12 weeks as measured by the proportion of subjects with sustained virologic response 12 weeks after cessation of treatment (SVR12)
- To evaluate the safety and tolerability by review of the accumulated safety data

The secondary objectives of this study are:

- To determine the proportion of subjects who attain SVR at 4 and 24 weeks after cessation of treatment (SVR4 and SVR24)
- To evaluate the proportion of subjects with virologic failure
- To evaluate the emergence of viral resistance to SOF and VEL during treatment and after cessation of treatment

8.1.2. Primary Endpoint

The primary endpoint is SVR12 (HCV RNA < LLOQ 12 weeks after cessation of treatment) in the Full Analysis Set (FAS) population.

The primary safety endpoint is any AE leading to permanent discontinuation of study drug.

8.1.3. Secondary Endpoint

The secondary efficacy endpoints include the following:

- The proportion of subjects with HCV RNA < LLOQ at 4 and 24 weeks after cessation of treatment (SVR4 and SVR24)
- The proportion of subjects with virologic failure

8.2. Analysis Conventions

All individual subject data will be listed as measured. All statistical summaries and analyses will be performed using SAS® software (SAS Institute, Cary, North Carolina, USA).

The study drug in this study includes SOF/VEL FDC. Last dose of study drug refers to the last dose of SOF/VEL FDC and will be used in the definition of treatment-emergent AEs and laboratory abnormalities as well as the efficacy endpoints of SVR at various posttreatment time points.

8.2.1. Analysis Sets

8.2.1.1. Efficacy

The primary analysis set for efficacy analysis is defined as the Full Analysis Set (FAS) which includes all enrolled subjects who took at least 1 dose of study drug(s).

8.2.1.2. Safety

The primary analysis set for safety analyses will include all subjects who took at least 1 dose of study drug. Treatment-emergent data will be analyzed and defined as data collected from the first dose of the study drug through the date of last dose of the study drug plus 30 days.

8.3. Data Handling Conventions

Missing data can have an impact upon the interpretation of the trial data. Other than the endpoints discussed below, values for missing data will not be imputed.

For the analyses of categorical HCV RNA data, missing posttreatment HCV RNA data will have the missing data imputed. Missing on-treatment HCV RNA will have the missing data imputed up to the time of the last dose.

If a data point is missing and is preceded and followed in time by values that are "< LLOQ target not detected (TND)," then the missing data point will be set to "< LLOQ TND." If a data point is missing and preceded and followed by values that are "< LLOQ detected," or preceded by "< LLOQ detected" and followed by "< LLOQ TND," or preceded by "< LLOQ TND" and followed by "< LLOQ detected," then the missing value will be set to "< LLOQ detected." In these situations the data point will be termed a bracketed success;

otherwise, the data point will be termed a bracketed failure (ie, \geq LLOQ detected). If a data point is missing and is not bracketed, the missing data point will also be termed a failure (ie, \geq LLOQ detected) except for SVR24, which will be imputed according to the SVR12 status. Success for SVR12 who have no further HCV RNA measurements collected will be counted as a success for SVR24 due to the high correlation between these 2 endpoints.

Where appropriate, safety data for subjects that did not complete the study will be included in summary statistics. For example,

- If a subject took at least 1 dose of study drug, the subject will be included in a summary of AEs according to the treatment received; otherwise, if the subject is not dosed, then they will be excluded from the summary.
- If safety laboratory results for a subject are missing for any reason at a time point, the subject will be excluded from the calculation of summary statistics for that time point. If the subject is missing a pre-dose value, then the subject will be excluded from the calculation of summary statistics for the pre-dose value and the change from pre-dose values.

Values for missing safety laboratory data will not be imputed; however, a missing baseline result will be replaced with a screening result, if available. If no pretreatment safety laboratory value is available, the baseline value will be assumed to be normal (ie, no grade [Grade 0]) in the summary of graded laboratory abnormalities. Values for missing vital signs data will not be imputed; however, a missing baseline result will be replaced with a screening result, if available.

HCV RNA values below the LLOQ for the assay will be set to the lower limit minus 1 for calculation of summary statistics for the actual HCV RNA values and the change from baseline values by study visit. The reported values will be provided in the HCV RNA listing.

For selected analyses of early time point data, HCV RNA data (IU/mL) may be transformed to the logarithmic (base 10) scale (log₁₀ IU/mL).

8.4. Demographic Data and Baseline Characteristics

Demographic and baseline measurements will be summarized using standard descriptive methods.

Demographic summaries will include sex, race/ethnicity, and age.

Baseline characteristic data will include a summary of body mass index, HCV RNA level (log₁₀ IU/mL), genotype of HCV infection, IL28B genotype, and additional endpoints as necessary.

8.5. Efficacy Analysis

8.5.1. Primary Analysis

The primary efficacy endpoint for this study will be the proportion of subjects with SVR12, defined as HCV RNA < LLOQ 12 weeks after cessation of treatment. The primary analysis will be performed after all enrolled subjects have been followed through 12 weeks posttreatment or discontinued from study.

In the primary efficacy analysis, the SVR12 rate in FAS will be compared to the efficacy threshold rate of 78% (described in Section 8.7.1) using a two-sided exact one-sample binomial test at significance level of 0.05: ie, the hypothesis for superiority is as follows:

H0: SVR12 rate = 78%,

H1: SVR12 rate \neq 78%

In addition, a point estimate with a two-sided 95% exact confidence interval using the binomial distribution (Clopper-Pearson method) will be constructed for the SVR12 rate.

A success for the primary endpoint will be claimed if the following criterion is met: point estimate of SVR12 is statistically significantly higher than 78% by a two-sided exact one-sample binomial test at significance level 0.05, ie, p-value for above hypothesis testing for superiority is ≤ 0.05 .

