8.7.2. Determination of Sample Size on Basis of Threshold

This study intends to enroll patients who have compensated cirrhosis. A sample size of approximately 36 compensated cirrhotic Japanese subjects in the study will provide > 80% power to demonstrate superiority to a performance threshold of 78%, assuming an expected SVR12 rate of 96% with 12 weeks of SOF/VEL therapy (based on a two-sided exact one-sample binomial test of superiority at a significance level of 0.05). This expected 96% SVR12 rate, based on the observed SVR12 rate in ASTRAL-1 (GS-US-342-1138) for GT1b compensated cirrhotic subjects, represents a clinically relevant response for compensated cirrhotic patients,

who are at risk of PI-based liver toxicity and currently have no highly-effective PI-free pangenotypic treatment options.

9. **RESPONSIBILITIES**

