1.3. Sample Size and Power

A sample size of approximately 36 compensated cirrhotic Japanese subjects in the study will provide > 80% power to demonstrate superiority to a performance threshold of 78%, assuming an expected SVR12 rate of 96% with 12 weeks of SOF/VEL therapy (based on a 2-sided exact 1-sample binomial test of superiority at a significance level of 0.05)

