6.1.2. Statistical Hypothesis for the Primary Efficacy Endpoint

In the primary efficacy analysis, the SVR12 rate in FAS will be compared to the pre-specified efficacy threshold of 78% using a 2-sided exact 1-sample binomial test at the 0.05 significance level. The null (H0) and alternative (H1) hypotheses used to assess the superiority of SOF/VEL relative to the performance goal of 78% as follows:

H0: SVR12 rate = 78%

H1: SVR12 rate \neq 78%

In addition, a point estimate with a 2-sided 95% exact confidence interval (CI) using the binomial distribution (Clopper-Pearson method) {Clopper 1934} will be constructed for the SVR12 rate.

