6.1.3. Primary Analysis of the Primary Efficacy Endpoint

The 2-sided 1-sample binomial test will be used to test the statistical hypothesis described above. The 2-sided 95% exact CI based on the Clopper-Pearson method will be provided for the SVR12 rate

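### Does leaving the two-sided exact binomial p-value undefined make the primary success rule ambiguous at 33 of 36 responders?

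*Protocol*

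**What the plan says.** Protocol 8.5.1 compares the SVR12 rate in the Full Analysis Set (FAS) with 78% "using a two-sided exact one-sample binomial test at significance level of 0.05". The null is a rate equal to 78% and the alternative is a rate different from 78%. Success is claimed if the "point estimate of SVR12 is statistically significantly higher than 78% by a two-sided exact one-sample binomial test at significance level 0.05", that is, if p is at most 0.05. The Synopsis and Protocol 8.7.1 repeat this criterion. The same section of the protocol then adds the interval: "In addition, a point estimate with a two-sided 95% exact confidence interval using the binomial distribution (Clopper-Pearson method) will be constructed".

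Protocol 8.5.2 leaves further efficacy detail to the SAP. SAP 6.1.2 restates the comparison "using a 2-sided exact 1-sample binomial test at the 0.05 significance level" with the same hypotheses, and the same Clopper-Pearson interval follows directly. SAP 6.1.3 says only: "The 2-sided 1-sample binomial test will be used to test the statistical hypothesis described above". SAP 6.4 declares no change from the protocol, and SAP 9 names SAS 9.4 without a procedure.

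On size, SAP 1.3 states: "A sample size of approximately 36 compensated cirrhotic Japanese subjects in the study will provide > 80% power". Protocol 8.7.2 gives the inputs: "superiority to a performance threshold of 78%, assuming an expected SVR12 rate of 96% with 12 weeks of SOF/VEL therapy".

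Neither document says how the two-sided p-value is formed or gives a critical number of responders.

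**The concern.** A two-sided exact p-value is unique only when the null distribution is symmetric. At a null rate of 78% it is skewed, and two constructions are in common use:

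- **Doubled tail:** twice the smaller tail probability.
- **Minimum likelihood:** the total probability of all outcomes no more likely than the one observed.

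At 36 subjects, the planned number, the two give opposite verdicts at 33 responders. The success rule cites only the p-value, and the Clopper-Pearson interval is reported in addition to it. On the text alone, a report could claim superiority to 78% beside a 95% interval that includes 78%. The trial is single-arm and open-label and has one confirmatory test, so a pass/fail answer that depended on an unstated software convention would be uncomfortable. The minimum-likelihood version also puts 2.9% in the upper tail, more than half of 0.05.

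**Working it through.** **Inputs.** n = 36, null rate 0.78, assumed rate 0.96 and two-sided level 0.05 (Protocol 8.5.1 and 8.7.2; SAP 1.3). X is the number of responders. Missing SVR12 values that are not bracketed count as failures (Protocol 8.3; SAP 3.5.1), so the denominator stays the FAS.

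**1. The plan's own figure.** At 0.96:

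- P(X = 36) = 0.96^36 = 0.2300
- P(X = 35) = 36 × 0.96^35 × 0.04 = 0.3450
- P(X = 34) = 630 × 0.96^34 × 0.04² = 0.2516
- P(X = 33) = 7140 × 0.96^33 × 0.04³ = 0.1188

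A rule of at least 34 has power 0.2300 + 0.3450 + 0.2516 = 0.8266. A rule of at least 33 has power 0.8266 + 0.1188 = 0.9454. The stated power above 80% is reproduced under either rule.

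**2. Two-sided p-values at 33/36 under 0.78.** The upper tail is P(X ≥ 33) = 0.02889.

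- Doubled tail: 2 × 0.02889 = 0.0578, not significant.
- Minimum likelihood: P(X = 33) = 0.02090. In the lower tail, P(X = 22) = 0.00999 is smaller, but P(X = 23) = 0.02155 is larger, so the lower part is P(X ≤ 22) = 0.01636. The sum is 0.02889 + 0.01636 = 0.04525, significant.

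**3. Neighbouring counts and the planned interval.**

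| Responders | Doubled-tail p | Minimum-likelihood p | Clopper-Pearson lower limit |
|---|---|---|---|
| 32/36 | 0.155 | 0.157 | 73.9% |
| 33/36 | 0.0578 | 0.0452 | 77.5% |
| 34/36 | 0.0160 | 0.0144 | 81.3% |

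Only 33/36 divides the two versions.

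**4. Which version matches the interval.** The Clopper-Pearson lower limit L for k responders solves P(X ≥ k given L) = 0.025. So L exceeds 0.78 when P(X ≥ k given 0.78) is below 0.025, which is when twice that tail is below 0.05. The doubled-tail test and the planned interval therefore cannot disagree. At n = 36 both require at least 34, because P(X ≥ 34) = 0.00799 is below 0.025 and P(X ≥ 33) = 0.02889 is above it.

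**5. Two-sided size at n = 36.** Both versions reject below at 22 or fewer.

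- Doubled tail: 0.01636 + 0.00799 = 0.0243
- Minimum likelihood: 0.01636 + 0.02889 = 0.0452

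Both are within the stated 0.05.

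**6. How often it matters.** If the FAS is exactly 36, the chance of exactly 33 responders is 11.9% at a true rate of 96%, 16.4% at 95% and 20.0% at 94%. Only 96% is the plan's assumption. At n = 35 both versions need 33, and at n = 37 both need 34. Over n = 30 to 45 the critical counts differ only at 30, 36 and 43.

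**The case for a change.** The best case for a change is that 36 is the planned number. The success criterion mentions only the p-value, and the rule for the single confirmatory test should be settled before anyone sees the data. Three non-responders among 36, whether from relapse or from missing post-treatment samples, would put the trial on the disputed count. The stated power does not settle the matter. Although 82.7% is closer to the stated bound than 94.5%, both satisfy it, and every size from 31 to 36 gives more than 80% under either version. Requiring a significantly higher rate does not settle it either, since 33/36 is 91.7% and lies above 78% under both.

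Much of this stands. No sentence excludes the minimum-likelihood construction, and at one count it would give a claim at odds with the reported interval.

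The complaint about type I error does not stand. The plan states a two-sided level of 0.05 against a two-sided alternative, and both versions respect it. Neither document sets a one-sided limit of 2.5%. The 11.9% figure is also conditional on the FAS being exactly 36. Enrolment is only approximately 36, and the FAS excludes subjects never dosed. The unconditional chance is lower and cannot be computed from the documents.

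**Conclusion.** No change to the plan is needed. This is missing detail that the plan's own choices fill. Protocol 8.5.1 and SAP 6.1.2 each put the test and a two-sided 95% Clopper-Pearson interval together, and that interval is the inversion of the doubled-tail test. With a superiority claim in one direction, an analyst would use the matching version. At n = 36 that means at least 34 responders, upper-tail error 0.80% and power 82.7%, in line with the stated power. Test and interval then always agree.

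The contradiction arises only if three things coincide: a p-value that does not match the stated interval, an FAS of exactly 36, and exactly 33 responders. Given an FAS of 36, that last event has probability 11.9% at the assumed 96% and 2.1% at the null rate of 78%. Even then the two-sided error level holds, at 0.0452.

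The null rate, level, threshold, analysis set, missing-data rule and power statement are all prespecified, and none is shown to be wrong. Writing the convention down would record what the pairing already implies and would alter no planned figure. The conclusion rests on reading the test and the interval as a pair. The text supports that reading but does not state it.

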8.5.2. Secondary Analyses

The proportion of subjects with HCV RNA below LLOQ over time (including SVR endpoints) will be presented in tabular and graphical form.

Descriptive summaries and listings will be provided for efficacy evaluation of the proportion of subjects who experience virologic failure and additional efficacy evaluations including HCV RNA values and change from baseline through end of treatment.

Details on efficacy analyses will be described in the statistical analysis plan.

8.6. Safety Analysis

Safety will be evaluated by assessment of clinical laboratory tests, physical examinations, and vital signs measurements and AEs will be documented at various time points during the study.

All safety data collected, on or after the first dose of the study drug administration up to 30 days after the last dose of the study drug will be summarized.

